5.5. Investigational Product Storage

The investigator, or an approved representative, eg, pharmacist will ensure that all investigational products are stored in a secured area with controlled access under required storage conditions and in accordance with applicable regulatory requirements.

Investigational products should be stored in their original containers and in accordance with the labels.

Upon receipt at the site, all drug product should be immediately transferred, in its original container, to the appropriate monitored storage area. Current storage conditions for

AdC68 vials are frozen (-20°C±5°C). The current storage conditions for the pDNA, tremelimumab and sasanlimab are refrigerated (2-8°C).

Any storage conditions stated in the SRSD will be superseded by the storage conditions stated on the product label. Please see the Instructions for Use for details on storage of the TDS-IM device.

Site systems must be capable of measuring and documenting (for example, via a log), at a minimum, daily minimum and maximum temperatures for all site storage locations (as applicable, including frozen, refrigerated, and/or room-temperature products). This should be captured from the time of investigational product receipt throughout the study. Even for continuous monitoring systems, a log or site procedure that ensures active evaluation for excursions should be available. The intent is to ensure that the minimum and maximum temperature is checked each business day to confirm that no excursion occurred since the last evaluation and to provide the site with the capability to store or view the minimum/maximum temperature for all nonworking days upon return to normal operations. The operation of the temperature monitoring device and storage unit (for example, refrigerator), as applicable, should be regularly inspected to ensure they are maintained in working order.

Any excursions from the product label storage conditions should be reported to Pfizer upon discovery. The site should actively pursue options for returning the product to the storage conditions described in the labeling, as soon as possible. Deviations from the storage requirements, including any actions taken, must be documented and reported to Pfizer.

Once an excursion is identified, the investigational product must be quarantined and not used until Pfizer provides permission to use the investigational product. It will not be considered a protocol deviation if Pfizer approves the use of the investigational product after the temperature excursion. Use of the investigational product prior to Pfizer approval will be considered a protocol deviation. Specific details regarding information the site should report for each excursion will be provided to the site.

5.6. Investigational Product Accountability

The investigator site must maintain adequate records documenting the receipt, use, loss, or other disposition of the investigational product supplies. All investigational products will be accounted for using a drug accountability form/record.

5.6.1. Destruction of Investigational Product Supplies

The sponsor or designee will provide guidance on the destruction of unused investigational product (eg, at the site). If destruction is authorized to take place at the investigator site, the investigator must ensure that the materials are destroyed in compliance with applicable environmental regulations, institutional policy, and any special instructions provided by Pfizer, and all destruction must be adequately documented.

5.7. Concomitant Treatment(s)

Concomitant treatment considered necessary for the participant's well-being may be given at discretion of the treating physician.

All concomitant treatments, blood products, as well as nondrug interventions received by participants from screening until the end of study visit will be recorded on the CRF.

5.7.1. Prohibited Concomitant Vaccines

No vaccines (licensed or investigational) other than study vaccine, influenza, COVID-19 and pneumococcal vaccines should be given during the study within 30 days prior to or after dosing. Other vaccines may be administered only if medically necessary (eg, tetanus post exposure prophylaxis).

For participants who receive tremelimumab, live attenuated vaccines should not be administered within 30 days prior to or after dosing with tremelimumab. The administration of inactivated vaccines are allowed.

5.7.2. Other Anti-tumor/Anti-Cancer or Experimental Drugs

No additional anti-tumor treatment will be permitted while participants are receiving study treatment. Additionally, the concurrent use of select vitamins or herbal supplements is not permitted

5.7.3. Supportive Care

Palliative and supportive care for disease related symptoms may be administered at the investigator's discretion and according to any available American Society of Clinical Oncology (ASCO) guidelines.

Participants currently being treated with denosumab or bisphosphonates (eg, zoledronate) for bone disease may continue treatment while participating in this study. However, initiation of treatment with these types of compounds should be avoided while participating in the study.

Palliative radiotherapy on study is permitted for the treatment of painful bony lesions providing the lesions were known at the time of study entry and the investigator clearly indicates that the need for palliative radiotherapy is not indicative of disease progression.

Participants currently being treated with a gonadotropin-releasing hormone agonist (GnRH agonist) may continue treatment while on clinical study C3621001 as long as the GnRH agonist treatment has been well tolerated for at least 3 months prior to study entry.

5.7.4. Hematopoietic Growth Factors

Primary prophylactic use of granulocyte-colony stimulating factors is not permitted during Cycle 1, but they may be used to treat treatment emergent neutropenia as indicated by the current American Society of Clinical Oncology guidelines.²

Erythropoietin may be used at the investigator's discretion for the supportive treatment of anemia.

5.7.5. Anti-Diarrheal, Anti-Emetic Therapy

Primary prophylaxis of diarrhea, nausea and vomiting is not permitted prior to the first dose of AdC68, tremelimumab and/or sasanlimab. Primary prophylaxis on subsequent dosing days is at the investigator's discretion. The choice of the prophylactic drug is up to the investigator with sponsor approval and assuming the drug is not prohibited as specified in [Section 5.7](#), as well as the duration of treatment assuming there is no known or expected drug-drug interaction. If so, then it must be approved by the sponsor.

5.7.6. Anti-Inflammatory Therapy

Anti-inflammatory or narcotic analgesic may be offered as needed assuming there is no known or expected drug-drug interaction and assuming the drug is not included in the Concomitant Treatment(s) [Section 5.7](#).

5.7.7. Corticosteroids

Chronic, systemic corticosteroid use for palliative or supportive purpose is not permitted. The short term use of corticosteroids (eg, 5 mg q.d. of prednisone for 2 weeks) as symptomatic treatment on an individual basis and upon discussion with the sponsor is allowed. Acute emergency administration, topical applications, inhaled sprays, eye drops, or local injections of corticosteroids are allowed.

5.7.8. Surgery

Caution is advised on theoretical grounds for any surgical procedures during the study. The appropriate interval of time between surgery and administration of VBIR-2 required to minimize the risk of impaired wound healing and bleeding has not been determined. Stopping all components of VBIR-2 is recommended at least 7 days prior to surgery. Postoperatively, the decision to reinitiate treatment should be based on a clinical assessment of satisfactory wound healing and recovery from surgery.

6. STUDY PROCEDURES

6.1. Screening

For screening procedures see the [Schedule of Activities](#) and [ASSESSMENTS](#) sections.

6.2. Study Period

For the treatment period procedures, see the [Schedule of Activities](#) and [ASSESSMENTS](#) sections.

6.3. End of Treatment

The End of treatment visit will be completed at the time point when a decision is made to discontinue study treatment. This can occur during Cycles 1 or 2 or during the Maintenance

Treatment Phase of the study. Obtain the specified EOT assessments (see [Schedule of Activities](#)) if not completed in the past two weeks (past 6 weeks for tumor assessments).

6.4. Follow-up

For follow-up procedures see the [Schedule of Activities](#) and [ASSESSMENTS](#) sections.

6.5. Survival Follow-up

After treatment discontinuation, participant survival status will be collected every 3 months until death, participant refusal, or lost to follow-up (telephone contact acceptable).

6.6. Participant Withdrawal

Withdrawal of consent:

Participants who request to discontinue receipt of study treatment will remain in the study and must continue to be followed for protocol specified follow-up procedures. The only exception to this is when a participant specifically withdraws consent for any further contact with them or persons previously authorized by the participant to provide this information. Participants should notify the investigator in writing of the decision to withdraw consent from future follow-up, whenever possible. The withdrawal of consent should be explained in detail in the medical records by the Investigator, as to whether the withdrawal is only from further receipt of investigational product, or also from study procedures and/or posttreatment study follow-up; this information should be entered on the appropriate CRF page. In the event that survival status (whether the participant is alive or dead) is being measured, and if publicly available information is part of the origin of this data, it is important that collecting this information should be carried out only as appropriately directed in accordance with local law.

Lost to follow-up:

All reasonable efforts must be made to locate participants to determine and report their ongoing status. This includes follow-up with persons authorized by the participant as noted above. “Lost to Follow-up” is defined by the inability to reach the participant after a minimum of 2 documented phone calls, faxes, or e-mails as well as lack of response by the participant to 1 letter sent by registered mail. All attempts should be documented in the participant’s medical records. If it is determined that the participant has died, the site will use locally-permissible methods to obtain the cause and the date of death. If the investigator’s use of a third-party representative to assist in the follow-up portion of the study has been included in the participant’s informed consent, then the Investigator may use a sponsor-retained third-party representative to assist site staff with obtaining the participant’s contact information or other public survival status data necessary to complete the follow-up portion of the study. The site staff and representative will consult publicly available sources, such as public health registries and databases, in order to obtain updated contact information. If, after all attempts, the participant remains lost to follow-up, then the last-known-alive date

as determined by the Investigator should be reported and documented in the participant's medical records.

Participants may withdraw from treatment at any time at their own request, or they may be withdrawn at any time at the discretion of the investigator or sponsor for safety (see also the [Withdrawal From the Study Due to Adverse Events \(see also the Participant Withdrawal Section\)](#) or behavioral reasons, or the inability of the participant to comply with the protocol-required schedule of study visits or procedures at a given investigator site.

Reasons for withdrawal of study treatment may include:

- Objective disease progression;
- Global deterioration of health status requiring discontinuation;
- Unacceptable toxicity;
- Pregnancy;
- Significant protocol violation;
- Lost to follow-up;
- Participant refused further treatment;
- Study terminated by sponsor;
- Death.

Reasons for withdrawal from study follow-up may include:

- Completed study follow-up;
- Study terminated by sponsor;
- Lost to follow-up;
- Refused further follow-up;
- Death.

If a participant does not return for a scheduled visit, every effort should be made to contact the participant. All attempts to contact the participant and information received during contact attempts should be documented in the participant's medical record. Regardless of the circumstance, every effort should be made to document participant outcome, if possible. The Investigator should inquire about the reason for withdrawal, request that the participant

return for a final visit, if applicable, and follow-up with the participant regarding any unresolved AEs.

If the participant refuses further visits, the participant should continue to be followed for survival (if survival is a secondary endpoint) unless the participant withdraws consent for disclosure of future information or for further contact. In this case, no further study-specific evaluations should be performed and no additional data should be collected. The Sponsor may retain and continue to use any data collected before such withdrawal of consent.

7. ASSESSMENTS

Every effort should be made to ensure that the protocol-required tests and procedures are completed as described. However, it is anticipated that occasionally there may be circumstances outside of the control of the investigator that may make it unfeasible to perform the test. In these cases the investigator must take all steps necessary to ensure the safety and well-being of the participant. When a protocol-required test cannot be performed, the investigator will document the reason for this and any corrective and preventive actions that he or she has taken to ensure that normal processes are adhered to as soon as possible. The study team will be informed of these incidents in a timely manner.

For samples being collected and shipped, detailed collection, processing, storage, shipment instructions and contact information will be provided to the investigator site prior to initiation of the study.

7.1. Safety Assessment

Safety assessments will include collection of AEs, serious adverse events (SAEs), vital signs and physical examination, electrocardiogram (ECG [12-lead]), laboratory assessments, including pregnancy tests and verification of concomitant treatments.

7.1.1. Pregnancy Testing

All pregnancy tests used in this study, either urine or serum, must have a sensitivity of at least 25 mIU/mL and must be performed by a certified laboratory. For female participants of childbearing potential, 2 negative pregnancy tests are required before receiving study treatment(s) (1 negative pregnancy test at screening and 1 at the baseline visit immediately before study treatment administration). Following a negative pregnancy test result at screening, appropriate contraception must be commenced and the second negative pregnancy test result will then be required at the baseline visit and within 5 days after the first day of the menstrual period (counting the first day of the menstrual period as Day 1) before the participant may receive the study treatment. In the absence of regular menstrual bleeding, the study candidate should have used 2 forms of contraception for at least 1 month before the second pregnancy test. Pregnancy tests will also be routinely repeated at (pre-dose) every cycle (Days 1, 29, 57, and 85) during the active treatment period, at the end of study treatment, at the 28-day Follow-Up visit to confirm that the participant has not become pregnant during the study. Pregnancy tests will also be done whenever 1 menstrual cycle is missed or when potential pregnancy is otherwise suspected, and may be repeated if requested

by institutional review boards (IRBs)/ethics committees (ECs) or if required by local regulations. In the case of a positive confirmed pregnancy, the participant will be withdrawn from administration of investigational product, but may remain in the study.

For female participants who achieved postmenopausal status and have not experienced their menses since at least 12 consecutive month, a serum FSH test must be conducted at screening only, in order to confirm a FSH level within the laboratory's reference ranges for post menopause.

7.1.2. Adverse Events

Assessment of adverse events will include the type, incidence, severity (graded by the NCI CTCAE version 5.0) timing, seriousness, and relatedness.

7.1.3. Laboratory Safety Assessment

Hematology and blood chemistry will be drawn at the time points described in the [Schedule of Activities](#) and analyzed at local laboratories.

Table 13. Safety Laboratory Tests

Hematology	Chemistry	Coagulation	Urinalysis	Pregnancy Test
Hemoglobin	ALT	PT or INR	Urine dipstick for urine protein: If positive collect 24-hr and microscopic (Reflex Testing)	For female participants of childbearing potential, serum or urine (see Section 7.1.1)
Platelets	AST	PTT		
WBC	Alk Phos			
Absolute Neutrophils	Sodium			
Absolute Lymphocytes	Potassium			
Absolute Monocytes	Magnesium		Urine dipstick for urine blood: If positive collect a microscopic (Reflex Testing)	
Absolute Eosinophils	Total Chloride			
Absolute Basophils	Total calcium			
	Total bilirubin ¹			
	BUN or Urea			
	Creatinine		Viral Tests ² (at Screening)	
	Uric Acid		Hepatitis B surface antigen ²	
	Glucose (nonfasted)		Hepatitis B core antibody ²	
	Albumin		Hepatitis C antibody ²	
	Phosphorous or Phosphate		Human immunodeficiency virus (HIV) ²	
	Lactate dehydrogenase			
	Lipase			
	Amylase			
	Bicarbonate or carbon dioxide			
	Total protein			
	TSH + reflex free T4 and free T3			

Table 13. Safety Laboratory Tests

Hematology	Chemistry	Coagulation	Urinalysis	Pregnancy Test
------------	-----------	-------------	------------	----------------

1. For potential Hy's Law cases, in addition to repeating AST and ALT, laboratory tests should include albumin, creatine kinase, total bilirubin, direct and indirect bilirubin, gamma-glutamyl transferase, prothrombin time (PT)/INR, alkaline phosphatase, total bile acids and acetaminophen drug and/or protein adduct levels.
2. Hepatitis B surface antigen, hepatitis B core antibody, hepatitis C antibody, and human immunodeficiency virus (HIV). Samples will be analyzed locally.

7.1.4. Vital Signs and Physical Examination

Participants will have a physical examination to include weight, vital signs, assessment of ECOG performance status and height; height will be measured at screening only.

A complete physical examination (PE) will be performed at Screening and at the End of Treatment visit for each participant and will include an assessment of all body systems. A neurologic examination must be conducted at Screening to look for potential signs of underlying autoimmune disorders. Findings of all physical examinations should be recorded in the source documents, and any change from baseline considered by the investigator to be clinically significant should be recorded as an adverse event in the CRF.

Abbreviated PEs should be performed as appropriate per the [Schedule of Activities](#) (SOA), and on an as needed basis for assessment of adverse events. Abbreviated exams should be targeted to specific symptoms or complaints and be consistent with local standard of care. However, a neurologic examination must be performed during each exam conducted during Cycle 1.

Weight and body surface area (BSA) do not need to be performed at each visit; however participants should be monitored throughout the study for significant weight change.

Vital signs should include measurements of blood pressure, pulse, and temperature (oral, temporal, tympanic or axillary). On dosing days, vital signs should be measured prior to administration of any of the study treatments. Sitting blood pressure (BP) and pulse after approximately 5 minutes rest should be measured with the participant's arm supported at the level of the heart and recorded to the nearest mmHg. The same arm should be used throughout the trial. A properly-sized and calibrated blood pressure cuff should be used to measure blood pressure. The use of automated devices for measuring BP is acceptable. Vitals signs, including temperature, pulse, and BP to be recorded 1-hour post-study drug administration during each Cycle on Days 1, 29, 57, and 85.

Assessment of the skin and subcutaneous tissue thickness at the eligible administration sites will be performed at screening as described in the TDS-IM V 2.0 Instructions for Use. The assessment procedure does not need to be repeated during the course of the study unless the participant experiences a greater than 10% change in body mass relative to screening.

7.1.5. (12-Lead) Electrocardiogram

Electrocardiogram machines to be utilized in this study will be supplied by a third party vendor.

At screening, a single 12-lead ECG tracing (with a 10-second rhythm strip) will be obtained. For Cycle 1 Day 1 and all subsequent specified time points (see [Schedule of Activities](#)), triplicate 12-lead ECG tracings (with a 10-second rhythm strip) will be obtained.

Generally, baseline and all corresponding time point ECGs should not be collected within 3 hours after food or beverage consumption and should be performed after the participant has rested quietly for at least 10 minutes in a supine position. All 12 lead ECGs should be confirmed by a qualified person at the institution and will be reviewed by a central laboratory.

At each time point, (see the [Schedule of Activities](#)), three consecutive ECGs will be performed at approximately 2 minutes apart to determine the mean QTcF interval. If the mean QTcF is prolonged (value of >500 msec), the ECGs should be re-evaluated by a qualified person at the institution for confirmation. If manual reading verifies a QTcF of >500 msec, immediate correction for reversible causes (including electrolyte abnormalities, hypoxia and concomitant medications for drugs with the potential to prolong the QTcF interval) should be performed. In addition, repeat ECGs should be immediately performed hourly for at least 3 hours until the QTcF interval falls below 500 msec. If QTcF interval reverts to less than 500 msec, and in the judgment of the investigator(s) and sponsor it is determined to be due to cause(s) other than investigational product, treatment may be continued with regular ECG monitoring. If in that timeframe the QTcF intervals rise above 500 msec the investigational product will be held until the QTcF interval decreases to 500 msec. Participants will then re-start the investigational product at the next lowest dose level. If the QTcF interval has still not decreased to 500 msec after 2-weeks, or if at any time a participant has a QTcF interval >515 msec or becomes symptomatic, the participant will be removed from the study. Additional triplicate ECGs may be performed as clinically indicated.

Prior to concluding that an episode of prolongation of the QTcF interval is due to investigational product, thorough consideration should be given to potential precipitating factors (eg, change in participant clinical condition, effect of concurrent medication, electrolyte disturbance) and possible evaluation by specialist.

If the participant experiences a cardiac or neurologic AE (specifically syncope, dizziness, seizures, or stroke), an ECG (triplicate) should be obtained at the time of the event.

Prior to concluding that an episode of prolongation of the QTcF interval is due to investigational product, thorough consideration should be given to potential precipitating factors (eg, change in participant clinical condition, effect of concurrent medication, electrolyte disturbance) and possible evaluation by specialist.

When matched with PK sampling, the ECG must be carried out before each PK sample drawing such that the PK sample is collected at the nominal time (ie, the timing of the PK collections over rides the timing of the ECG collections).

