7. Blood samples for determination of sasanlimab drug concentrations and for detection of ADA/NAb against sasanlimab will be collected as outlined in the [schedule of activities](#). Samples to be collected on dosing days are to be obtained within 6 hours prior to sasanlimab dosing.
8. For participants assigned to Cohorts 4A and 5A only.

SCHEDULE OF ACTIVITIES FOR DOSE EXPANSION (PART 2)

Protocol Activity	Screen ¹ (≤28 days)	Treatment Period												End of Treatment ³²	Post Treatment				Survival Follow-up ³⁴	
		Cycle 1						Cycle 2							Follow- Up (Months after EOT visit)					
Study Day		Day 1	Day 8	Day 15	Day 22	Day 29	Day 43	Day 57	Day 71	Day 85	Day 113				Month 1 ³³	Month 2	Month 4	Month 6	Post 6-Month Follow-up	
Cycle Day											Day 1	Day 29	Day 57	Day 85	Day 99		28 to 35 days			Every 3 Months
Visit Window (Days)*			±1	±2	±2	±2	±4	±2	±4	±2	±2	±2	±2	±2	±4		±4	±4	±4	±10
Informed consent ²	X																			
Tumor history ³	X																			
CCI																				
Medical history ⁷	X																			
Complete physical examination ⁸	X														X					
Abbreviated physical examination ⁸		X		X		X		X		X	X	X	X	X		X	X	X	X	
Assessment of skin thickness at administration sites ⁹	X																			
Height	X																			
Weight	X	X									X				X					
Vital signs ¹⁰	X	X	X	X	X	X		X		X	X	X	X	X	X	X	X	X	X	
Performance status ¹¹	X	X			X		X		X	X	X	X	X	X	X	X	X	X	X	
Laboratory																				
Unique Screening Labs ¹²	X																			
Hematology ¹³	X	X	X	X	X	X	X	X	X	X	X	X	X	X	X	X	X	X		
Blood Chemistry ¹⁴	X	X	X	X	X	X	X	X	X	X	X	X	X	X	X	X	X	X		
Coagulation ¹⁵	X			X		X		X		X					X	X				

PFIZER CONFIDENTIAL

Protocol Activity	Screen ¹ (≤28 days)	Treatment Period										End of Treatment ³²	Post Treatment				Survival Follow-up ³⁴			
		Cycle 1					Cycle 2						Follow- Up (Months after EOT visit)							
Study Day		Day 1	Day 8	Day 15	Day 22	Day 29	Day 43	Day 57	Day 71	Day 85	Day 113				Month 1 ³³	Month 2	Month 4	Month 6	Post 6-Month Follow-up	
Cycle Day											Day 1	Day 29	Day 57	Day 85	Day 99		28 to 35 days			Every 3 Months
Visit Window (Days)*		±1	±2	±2	±2	±4	±2	±4	±2	±2	±2	±2	±2	±2	±4	±4	±4	±10		
Cardiac Troponin-I (cTnI) ¹⁶	X				X		X		X		X									
Urinalysis ¹⁷	X			X		X		X		X	X	X	X	X	X	X				
Pregnancy Test or FSH Level (Serum) ¹⁸	X	X			X		X		X	X	X	X	X	X	X					
Contraception Check ¹⁹	X	X			X		X		X	X	X	X	X	X	X	X	X			
(12 lead) ECG ²⁰	X	X			X				X			X		X	X					
Registration																				
Registration ²¹		X																		

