30. **Serious and Non-serious Adverse Event Monitoring:** Adverse events should be documented and recorded at each visit using the National Cancer Institute Common Terminology Criteria for Adverse Events (NCI CTC AE) version 5.0. Participants must be followed for AEs for 6 months after the last study treatment administration or until all drug related toxicities have resolved, whichever is later; or earlier than 6 months should the participant commence another anticancer therapy in the meantime. The time period for actively eliciting and collecting AEs and SAEs ("active collection period") for each participant begins from the time the participant provides informed consent through and including 6 months after the last study treatment administration or until all drug related toxicities have resolved, whichever is later. If the participant begins a

Protocol Activity	Screen ¹ (≤28 days)	Treatment Period										Post Treatment						
		Cycle 1					Cycle 2					End of Treatment ³²	Follow- Up (Months after EOT visit)				Survival Follow-up ³⁴	
Study Day		Day 1	Day 8	Day 15	Day 22	Day 29	Day 43	Day 57	Day 71	Day 85	Day 113							Post 6-Month Follow-up
Cycle Day											Day 1	Day 29	Day 57	Day 85	Day 99	Every 3 Months		
Visit Window (Days)*			±1	±2	±2	±2	±4	±2	±4	±2	±2	±2	±2	±2	±4	±4	±4	±10

new anticancer therapy, the period for recording non-serious AEs on the CRF ends at the time the new treatment is started. However, any SAEs occurring during the active collection period must still be reported to Pfizer Safety and recorded on the CRF, irrespective of any intervening treatment.

31. **Concomitant Treatments:** All concomitant medications and non-drug supportive interventions should be recorded in the CRF.
32. **End of Treatment Visit:** The End of treatment visit will be completed at the time point when a decision is made to discontinue study treatment. This can occur during Cycles 1 or 2 or during the Maintenance Treatment Phase of the study. Obtain these assessments if not completed in the past 2 weeks (past 6 weeks for tumor assessments).
33. **Follow up:** At least 28 days, and no more than 35 days after discontinuation of study treatment, participants will return to complete the required assessments. Participants will then return at Month 2, Month 4 and Month 6 to complete the required assessments.

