5.4.5.2. Tremelimumab Dose Reductions

Changes in the dose levels for tremelimumab will be discussed with the sponsor. A dose reduction of tremelimumab by 1 dose level (from 80 mg to 40 mg) may be allowed depending on the type and severity of toxicity encountered. In addition, an intermediate dose may be considered. Participants requiring a dose level lower than 40 mg will be discontinued from treatment and enter into the follow-up phase unless otherwise agreed between the investigator and sponsor. Algorithms for the management of suspected pulmonary,

gastrointestinal (GI), liver, endocrine, skin, neurological and renal toxicities have been developed (See [Appendix 5](#)). All dose modifications/adjustments must be clearly documented in the participant's source notes and case report form (CRF).

Once a dose has been reduced for a given participant, all subsequent cycles should be administered at that dose level, unless further dose reduction is required. Dose re-escalation for tremelimumab is not allowed.

Table 7. Tremelimumab Available Dose Levels (Part 1)

Dose Level	Tremelimumab
Starting	40 mg
+1	80 mg

Table 8. Tremelimumab Available Dose Levels (Part 2)

Dose Level	Tremelimumab
Starting	80 mg
-1	40 mg

Table 9. Dose Modifications for Tremelimumab Related Toxicity When Given in Combination with AdC68 and pDNA

Toxicity	Grade 1	Grade 3	Grade 4
Non-hematologic	Continue at the same dose level.	Withhold dose until toxicity is Grade ≤ 1 , or has returned to baseline, then resume treatment at the same dose level or reduce the dose by 1 level at the discretion of the investigator.*	Discontinue treatment.
Hematologic	Continue at the same dose level.	Withhold dose until toxicity is Grade ≤ 2 , or has returned to baseline, then resume treatment at the same dose level.	Discontinue treatment.

* Nausea, vomiting, or diarrhea must persist at Grade 3 despite maximal medical therapy to require dose modification.

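### Protocol 7.1.5 removes participants with marked QTcF prolongation from the study; read literally, this conflicts with the safety and survival follow-up rules, none of which has a QTcF exit

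*Protocol*

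**What the plan says.** Protocol 7.1.5 (12-Lead Electrocardiogram) sets out graded steps for a confirmed QTcF above 500 msec. The intermediate step acts on dosing: "the investigational product will be held until the QTcF interval decreases to 500 msec", after which dosing restarts at a lower level. The last step has three triggers: QTcF still not down to 500 msec after two weeks, QTcF above 515 msec at any time, or symptoms. Its wording changes from product to study: "if at any time a participant has a QTcF interval >515 msec or becomes symptomatic, the participant will be removed from the study". SAP 6.2.5 repeats the sentence.

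The follow-up rules for treated participants are set elsewhere in the protocol:

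- Schedule of Activities, Part 2, footnote 30: "Participants must be followed for AEs for 6 months after the last study treatment administration or until all drug related toxicities have resolved". The longer of these two periods applies. The one early exit named is the start of another anticancer therapy.
- Section 8.1.4: adverse events and serious adverse events are actively collected for at least six months after the last dose. The one exception listed there is screen failure.
- Section 3.1.2 and Schedule of Activities, Part 2, footnote 33: stopping treatment leads into a six-month post-dose follow-up. After the first visit at 28 to 35 days, "Participants will then return at Month 2, Month 4 and Month 6 to complete the required assessments".
- Section 6.5: survival status is collected every three months until death, refusal or loss to follow-up.

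**The concern.** In most trials, stopping a drug for toxicity and leaving the study are different events, and the first should not cause the second. Section 7.1.5 appears to merge them at its most serious step. Participants who reach that step have a persistent or marked QTcF prolongation, or symptoms, and they are the ones whose later course matters most for judging cardiac safety.

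If a site acted on the words alone, it could close the participant's record without the later adverse event visits and survival contacts. Under Section 2.2, adverse events are a Part 2 primary endpoint and overall survival is a secondary endpoint, so both kinds of information are wanted. The 500 and 515 msec thresholds and the follow-up design are not in question.

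**Working it through.** No arithmetic applies. The check has three parts.

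**1. Does any follow-up rule release a participant because of QTcF?**

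| Rule | What ends it | QTcF exit? |
|---|---|---|
| AE follow-up (Schedule of Activities, Part 2, footnote 30) | Six months, or resolution of drug-related toxicity if later; earlier if new anticancer therapy starts | None |
| AE/SAE collection (8.1.4) | At least six months after the last dose; screen failures excepted | None |
| Post-dose follow-up (3.1.2) | End of the six-month period | None |
| Survival follow-up (6.5) | Death, refusal, loss to follow-up | None |

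A participant removed under 7.1.5 who has not refused contact, been lost or died is therefore still owed all four. A site cannot carry out the literal 7.1.5 instruction and these rules together, and the protocol does not say which prevails.

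**2. Does the protocol separate treatment from study elsewhere?** In several places it does:

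- Pregnancy (7.1.1): "the participant will be withdrawn from administration of investigational product, but may remain in the study".
- Tremelimumab needed at less than 40 mg (5.4.5.2), unless investigator and sponsor agree otherwise: the participant "will be discontinued from treatment and enter into the follow-up phase".
- A participant who asks to stop treatment (6.6) "will remain in the study and must continue to be followed for protocol specified follow-up procedures".
- Myocarditis, the nearest cardiac comparator (Table 12 footnote and Appendix 5): the instruction is permanent discontinuation of treatment.
- Section 6.6 lists unacceptable toxicity as a reason for withdrawing treatment and gives no toxicity reason for leaving follow-up. Both lists are illustrative, not exhaustive.

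**3. Does it also use study loosely?** It does:

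- Section 5.4.5.3 and the Table 12 footnote tie staying in the study to continued dosing.
- Section 8.1.3 speaks of withdrawal from the study because of adverse events, and 6.6 cross-refers to it from a sentence about withdrawal from treatment.
- Section 8.2.2 refers to a test result that leads to discontinuation from the study.

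The literal conflict in part 1 is plain. Parts 2 and 3 show that usage is mixed, so the intended meaning of 7.1.5 has to be inferred. Treatment discontinuation is the likelier meaning.

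**The case against.** The strongest reply is that this is one loosely chosen word, and that many other rules would keep the participant under observation. That reply has substance. Beyond the follow-up rules above:

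- Section 8.2.2 makes a test result that leads to discontinuation, or that needs further diagnostic testing, a recordable adverse event.
- Section 8.1 obliges the investigator to establish the outcome of each event.
- Section 8.1.4.1 continues follow-up of serious adverse events until they resolve or stabilise.
- Section 6.6 asks for every effort to document outcome, for a final visit where applicable and for follow-up of unresolved adverse events. It also continues survival follow-up for participants who refuse visits, unless they withdraw consent for disclosure of future information or for further contact.
- The sentence in 7.1.5 straight after the disputed one allows further triplicate ECGs when clinically indicated.

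Together these make loss of follow-up unlikely at a site that reads the whole protocol. They do not remove the conflict. The ECG section is the specific instruction a site consults when a QTcF alert arrives, its wording is mandatory, and 8.1.3 shows that leaving the study because of an adverse event is a recognised idea in this protocol. The rule in 6.6 that participants remain in the study is written for those who ask to stop, so it serves as a contrast and does not govern this case.

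A reader might infer that the protocol otherwise keeps treatment and study strictly apart, so that 7.1.5 must be a deliberate exit. Sections 5.4.5.3, 8.1.3 and 8.2.2 do not support that.

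**Conclusion.** The conflict is real as a matter of wording, and it is minor. Section 7.1.5 read literally cannot be reconciled with the safety and survival follow-up rules. The likely intent is to stop treatment and keep following the participant.

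This rests on two assumptions: that the participant has been dosed and has not withdrawn consent for contact, and that a site might act on the ECG section by itself.

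No size can be put on it. The documents give no expected rate of QTcF above 515 msec, so neither a count nor a word such as few has a source. The scheduled visits and contacts after treatment could be counted, but that would describe the calendar and would not measure an effect.

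Two further inferences are not supported. One is that safety or survival results will be biased, since nothing in the documents shows that follow-up would in fact be lost. The other is that sample size, error rates or planned analyses are affected, since none of them depends on this sentence.

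**What to change.** In Protocol 7.1.5, change the last step so that the participant is *permanently discontinued from study treatment and followed per Sections 6.3, 6.4, 6.5 and 8.1.4*. Leave the thresholds and the earlier steps as they are.

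The cost is one sentence. The End of Treatment visit, the follow-up visits and the survival contacts already exist, and 7.1.5 already permits additional ECGs. Making the same change in SAP 6.2.5 is optional: that section repeats conduct text from the protocol, and the protocol is what sites follow.
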